8.1.5 Primary Efficacy Analysis

A 90% two-sided confidence interval will be computed for the success rate at 2 years. If the lower bound of the confidence interval is greater than 94.7%, then the non-inferiority hypothesis will be supported; that is the 2 year success rate is non-inferior to 97.2% with a margin of 2.5%. If the lower bound of the confidence interval is greater than 97.2% then it is supported that the 2 year success rate is superior to 97.2%.

The Kaplan-Meier survival curve of revision/removal of femoral or tibial cone augment will be displayed using SAS/PROC LIFETEST.

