	System with at least one Triathlon Tritanium Cone Augment. The	
	clinical outcomes of Triathlon Tritanium Cone Augments will be	
	compared to published literature and data collected in the Triathlon TS	
	Outcomes Study.	
	1. Follow-up of each revision TKA case to 5 years	
Study Duration	2. Enrollment period of 48 months	
	3. Approximate 10-year total duration	
Number of Centers	8 to 12 investigational centers	
	The revision rate of the Triathlon Tritanium Cone Augments is expected	
Hypothesis	to be less than 2.8% for a septic loosening ^{$1,2$} of either the Femoral or the	
	Tibial Cone Augments at 2 years postoperative.	

	Primary:
	To evaluate the success rate of the Triathlon Tritanium Cone Augment
	with the Triathlon TS Total Knee System at 2 years postoperative,
	defined as absence of revision of the Femoral Cone Augment or Tibial
	Cone Augment for aseptic loosening.
	Secondary:
	To evaluate unexpected end-of-stem pain with regards to the
	Triathlon Tritanium Cone Augments location and severity and
Objectives	compare to published literature ³ at 2 years postoperative.
	To evaluate intraoperative bone defects using the Anderson
	Orthopaedic Research Institute (AORI) classification and correlate
	with the size and shape of cone implanted ^{6,7} .
	Exploratory:
	To evaluate the mean KSS objective knee scores at 2 years
	postoperative for cases which received the Triathlon TS Total Knee
	System with a Triathlon Tritanium Central Femoral Cone Augment.

	Function and health related quality of life (QOL) will be compared
	between the Triathlon TS with Triathlon Tritanium Cone Augments
	and published results for other revision knee systems with
	metaphyseal augments, as well as the Triathlon TS Outcomes
	Study using the following outcomes measures:
	 2011 Knee Society Score (KSS)⁹
	 Short Form-12 (SF-12)
	 Lower Extremity Activity Scale (LEAS)
	 Hospital for Special Surgery (HSS) Patella Score
Additional Data	 ○ EuroQuol 5D (EQ-5D)
Collection	 Follow-Up Questionnaire
	• Data collected at 6-week, 6-month, 1-year, 2-year, and 5-year
	visits will be compared to above mentioned controls with respect to
	improvement from preoperative scores.
	Radiographic stability, preoperative AORI classification and
	complications will be compared between those implanted with the
	Triathlon TS with Triathlon Tritanium Cone Augments and
	published results for other revision knee systems.
	Surgical details will be compared to data collected as part of the

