		excess of normal physiological requirements (e.g. > 30 days).
	J.	Patient has a failed unicondylar knee prosthesis.
	K.	Patient has a known sensitivity to device materials.
	L.	Patient is a prisoner.

	Primary Objective:
Statistical Methodology	 2-year success rate of the TS Total Knee System with Triathlon Tritanium Cone Augments with an endpoint of revision/removal of Femoral Cone Augment or Tibial Cone Augment for aseptic loosening will be compared with success of published literature on revision TKA with metaphyseal augments, with a 2.5% noninferiority margin. Secondary Objectives: The unexpected end-of-stem pain at 2 years will be tabulated separately for cases with femoral cone implanted only, tibial cone implanted only, both femoral and tibial cone implanted. The two way tables will have the level of shin pain as row variable and level of thigh pain as column variable. A two-way table of intraoperative AORI classification by femoral or tibial cone augment size will be presented
	 Exploratory Objective: The mean of KSS Objective Knee Score at 2 years postoperative for cases receive the Triathlon TS Total Knee System with a Triathlon Tritanium Central Femoral Cone Augment will be compared to 86 points with a 5 points noninferiority margin.

Evaluation Schedule

Evaluation	Preop X-rays (-1 yr) CRFs (-4 mos)	Intraop	6 weeks (+ 2 wks)	6 months ((+ 2 wks)	1 year (+ 2 mos)	2 years (+ 2 mos)	5 years (+ 2 mos)
Inclusion/Exclusion	x						
Demographics & Medical History	x						
Preoperative Functional Evaluation	x						
Previous Implant Information		Х					
Surgical Details		Х					
Postoperative Functional Evaluation			X	Х	Х	X	X
SF-12	Х		X	X	Х	X	X
LEAS	X		X	X	X	X	X
HSS Patella Score	X		X	X	X	X	Х
EQ-5D	X		X	X	X	X	X
Stem Tip Pain Diagram	Х*		x			х	x
*If applicable							
Radiographs:							
1. Bilateral* Anteroposterior (AP)							
X ^a . Long standing at pre-op and 6 weeks							
X ^b . Standard at 1 year, 2 years, and 5							
years	Va		Va	Yþ	Vþ	Yb	Yb
2. Mediolateral (ML)	~				•		•
3. Merchant (30° flexion)							
*Bilateral AP x-rays are preferred. Unilateral AP x-							
rays may be submitted if bilateral images are not							
available.							

X: Evaluation is required for all cases.

Functional Evaluation: The Functional Evaluations include the 2011 KSS, a standardized instrument with both surgeon completed, and patient reported sections that evaluate function, satisfaction, pain and motion.

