8.1.4 Primary Efficacy Hypothesis

The primary hypothesis to be tested will be that the success rate at 2 years postoperative with the Triathlon Tritanium Cone Augments is not worse than 97.2% with a non-inferiority margin of 2.5%. That is, the following hypothesis will be tested:

Ho: Pt <= 97.2% - 2.5% HA: Pt > 97.2% - 2.5%

Here, Pt is the success rate at 2 years postoperative with the Triathlon Tritanium Cone Augments. A case success at 2 years is defined as no incidence of revision/removal of femoral or tibial cone augment for aseptic loosening within 2 years.

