8.4.2 Sample Size Justification

For primary efficacy objective, based on the literature review^{1,2}, it is reasonable to have a reference value of 97.2% for success rate at 2 years. A case success at 2 years is defined as no incidence of revision/removal of femoral or tibial cone augment for aseptic loosening within 2 years.

Based on Triathlon TS Outcome Study, it is reasonable to assume the expected success rate at 2 years is 98.8%, 100 cases will be needed to have a power of 80% to detect that the 2 year success rate is non-inferior to 97.2% with a margin of 2.5% at 5% significance level. After factoring a 30% lost to follow-up rate, a total of 145 cases will be needed.

For exploratory efficacy objective among cases receive the Triathlon TS Total Knee System with a Triathlon Tritanium Central Femoral Cone Augment, based on the existing data of this study for non-femoral central cone, it is reasonable to have a reference value of 86 for the mean of KSS Objective Knee Score at 2 years postoperative, with a standard deviation of 10, 32 cases will be needed to have a power of 80% to identify the mean of KSS Objective Knee Score at 2 years postoperative is Non-Inferior to 86 with a noninferiority margin of 5 at 2.5% significance level. After factoring a 30% attrition rate, a total of 46 cases will be needed.

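### The Synopsis hypothesis (revision below 2.8%) is not what the primary test establishes (below 5.3%); the superiority rule that matches it is unsized and depends on an unnamed interval method

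*Combined protocol and SAP*

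**What the plan says.** The Hypothesis row of the Study Synopsis says that the revision rate is expected "to be less than 2.8% for a septic loosening" of either cone at 2 years (the extracted text splits the word aseptic). The Statistical Methodology row of the same Synopsis compares success with published literature "with a 2.5% noninferiority margin".

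Section 8.1.4 sets the formal hypotheses, in per cent: "Ho: Pt <= 97.2% - 2.5% HA: Pt > 97.2% - 2.5". Section 8.1.5 says: "A 90% two-sided confidence interval will be computed for the success rate at 2 years". A lower bound above 94.7% supports non-inferiority. A lower bound that "is greater than 97.2% then it is supported that the 2 year success rate is superior to 97.2" per cent is a second, stricter conclusion. No interval method is named for either.

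Section 8.4.2 takes 97.2% as the reference ("it is reasonable to have a reference value of 97.2% for success rate at 2 years"), assumes 98.8% success, and states that "100 cases will be needed to have a power of 80" per cent for non-inferiority at the 5% level. With 30% loss to follow-up this becomes 145 enrolled. It gives no sample size or power for superiority.

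**The concern.** The statement labelled as the hypothesis and the hypothesis tested differ by the whole margin. A non-inferiority pass could be read as confirming revision below 2.8% when it rules out only a rate 1.9 times as high (5.3 / 2.8).

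The superiority sentence is the only route to the 2.8% claim. With about 100 cases and an expected one or two failures, whether a lower bound clears a threshold this close to 100% depends heavily on how the interval is computed. If the method is chosen after the data are seen, the analyst in effect chooses the conclusion. One failure in 100 is superior by Wald and not superior by an exact interval.

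**Working it through.** **Inputs.** Reference 97.2%, margin 2.5 points, assumed success 98.8%, 100 evaluable and 145 enrolled (8.1.4, 8.4.2); 90% two-sided interval, so 5% in the lower tail (8.1.5); analysis of cases available at 2 years (8.4.4), so a simple binomial with X failures in n.

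**The plan's own figure.** The arcsine formula comes closest to 100 cases: n = [(1.645 + 0.842) / (2·asin√0.988 − 2·asin√0.947)]² = (2.486 / 0.2451)² = 103, with 79.0% power at n = 100. Inflation: 100 / 0.7 = 143, near the stated 145. The 80% is therefore a large-sample approximation and does not come from the decision rule of any particular interval. An exact binomial calculation gives 117.

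**The two thresholds.** Synopsis row: success above 100 − 2.8 = 97.2%. Tested: success above 97.2 − 2.5 = 94.7%, so revision below 5.3%.

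**Lower bounds at n = 100 (%).**

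| Failures | Clopper-Pearson | Wilson | Jeffreys | Wald |
|---|---|---|---|---|
| 0 | 97.05 | 97.37 | 98.10 | 100.00 |
| 1 | 95.34 | 95.64 | 96.16 | 97.36 |
| 2 | 93.84 | 94.14 | 94.58 | 95.70 |
| 3 | 92.43 | 92.73 | 93.12 | 94.19 |

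The exact bound with no failures is 0.05^(1/100) = 0.9705. The Wald bound with one failure is 0.99 − 1.645 × √(0.99 × 0.01 / 100) = 0.99 − 1.645 × 0.00995 = 0.9736.

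**Superiority rule (bound above 97.2%) at n = 100.**
- Clopper-Pearson: no possible result passes.
- Wilson and Jeffreys: zero failures only. Type I error 0.972^100 = 5.8%; power at 98.8% is 0.988^100 = 29.9%.
- Wald: up to one failure. Type I error P(X ≤ 1 | 2.8%) = 22.7%; power P(X ≤ 1 | 1.2%) = 66.2%.

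**Primary rule (bound above 94.7%) at n = 100.**
- Clopper-Pearson, Wilson and Jeffreys: up to one failure. Type I error P(X ≤ 1 | 5.3%) = 2.8%; power 66.2%.
- Wald: up to two failures. Type I error P(X ≤ 2 | 5.3%) = 9.5%; power 88.1%.

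**Other numbers of evaluable cases.**
- The exact superiority rule first becomes reachable when 0.05^(1/n) > 0.972: ln 0.05 / ln 0.972 = 105.5, so n = 106. One failure is first allowed at n = 168 (bound 97.21%; 97.19% at 167). From 106 to 167 it needs zero failures, which at 98.8% success has probability 27.8% at 106 and 17.4% at 145.
- Wald superiority type I error is 20.0% at 106 and 8.4% at 145.
- The exact primary rule first allows two failures at n = 117: type I error 4.9%, power 83.3%.
- Superiority with 80% power at 98.8% against 97.2% would need about 513 evaluable cases (exact).

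**The case against.** The Synopsis row states an expectation, which is consistent with the assumed 98.8% success. The margin appears in the same Synopsis, and 8.1.4 and 8.1.5 are explicit about H0, HA and the label attached to each conclusion. All of this stands. A reader might infer that the margin is concealed or that the formal hypothesis is in doubt, and the documents support neither. What remains is that the row headed Hypothesis carries a threshold that the primary test does not address.

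A reader might also infer that superiority is either impossible or carries a 23% false-positive rate. The documents do not support that either. They name neither Clopper-Pearson nor Wald, and Wilson and Jeffreys lie between the two: reachable, with type I error of 5.8%, close to nominal. Impossibility under the exact interval is also tied to about 100 evaluable cases. Enrolment is a minimum of 145 and the 30% loss is a planning assumption, so a loss of 27% or less (106 / 145 = 73% retained) makes the rule reachable.

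Finally, superiority is an unsized addition. Testing it after non-inferiority from the same interval needs no multiplicity adjustment, and its low power does not damage the primary conclusion. That is right. The unnamed interval does affect the primary conclusion, however, and naming the exact one has a power cost that must be disclosed.

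**Conclusion.** The point holds in this form: the Synopsis threshold (2.8%) differs from the tested one (5.3%), the superiority rule that would support 2.8% is unsized, and the unnamed interval decides its properties. At 100 evaluable cases the rule ranges from unattainable (Clopper-Pearson), through zero failures with 5.8% type I error and about 30% power (Wilson, Jeffreys), to 22.7% type I error (Wald). For the primary test, the choice moves type I error from 2.8% to 9.5% and power from 66% to 88%.

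This rests on a binomial analysis of cases evaluable at 2 years, on 5% in the lower tail even with zero failures, and on the plan's 98.8% for power. It does not question the margin, the 97.2% reference or the order of testing. The change should be made before the 2-year analysis, because it determines what may be concluded from zero, one or two failures.

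**What to change.** 1. Reword the Synopsis Hypothesis row to the tested hypothesis: 2-year cone revision for aseptic loosening below 5.3% (success above 94.7%), that is, non-inferior to 97.2% with a 2.5-point margin.
2. In 8.1.5, name the Clopper-Pearson 90% two-sided interval and rule out Wald.
3. Delete the superiority sentence, or state that it is unpowered and, with the exact interval, cannot be met below 106 evaluable cases and needs zero failures at 106 to 167.
4. In 8.4.2, restate primary power under the named interval: about 66% at 100 evaluable cases, and 83% at 117.

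The cost is wording, a more modest claim, and an openly lower primary power at the planned number. No new visits or data items are needed. If the sponsor wants at least 80% power under the exact rule, 117 evaluable cases means a loss of no more than 19% from 145 (28 / 145), or 117 / 0.7 = 167.1, so 168 enrolled at 30% loss.

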8.1.6 Secondary Efficacy Analyses

A two by two table of shin pain by thigh pain at 2 years will be created separately for cases with femoral cone augment implanted only; tibial cone augment implanted only; and both femoral cone augment and tibial cone augment implanted.

The intraoperative AORI classification and the size of the femoral or tibial cone augment will be tabulated.

8.1.7 Exploratory Efficacy Hypothesis

For cases which received the Triathlon TS Total Knee System with a Triathlon Tritanium Central Femoral Cone Augment, the exploratory hypothesis to be tested will be that the mean of KSS Objective Knee Score at 2 years postoperative is no worse than 86 with a non-inferiority margin of 5. The performance goal for 2-year KSS Objective Knee Score was calculated as 86 - 5 to give 81. That is, the following hypothesis will be tested:

H₀₁: u <=81 H_{A1}: u >81

Here, u is the mean KSS Objective Knee Score at 2 years postoperative.

8.1.8 Exploratory Efficacy Analysis

For cases which received the Triathlon TS Total Knee System with a Triathlon Tritanium Central Femoral Cone Augment, A 95% two-sided confidence interval for the mean of KSS Objective Knee Score at 2 years will be computed. If the lower bound of the confidence interval is greater than 81, then it is supported that KSS Objective Knee Score at 2 years is no worse than 86 with a non-inferiority margin of 5. If the lower bound of the confidence interval is greater than 86, then it is supported that KSS Objective Knee Score at 2 years is better than 86.

The analysis for the additional data collection is in 8.4.1 Data Summary.

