8.3 Missing Data

No missing data will be imputed.

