8.4.4 Analysis Population

Per Protocol Population: The study population for analysis will include all noncensored subjects who receive a Triathlon TS with Triathlon Tritanium Cone Augment and are available for efficacy evaluation at the 2-year primary endpoint. The primary and secondary efficacy analyses will be based on the per protocol population.

Safety Population: The safety population will include all non-censored subjects who received Triathlon TS with Triathlon Tritanium Cone Augment. The safety analysis will be based on the safety population.

9 Study Monitoring, Auditing, and Inspecting

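### The exploratory central-cone KSS test uses only available 2-year scores and sets aside the same score from three earlier visits, so loss related to those scores would bias it

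*Combined protocol and SAP*

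**What the plan says.** Section 8.1.7 sets a formal hypothesis for cases with a Central Femoral Cone Augment: "The performance goal for 2-year KSS Objective Knee Score was calculated as 86 - 5 to give 81". Section 8.1.8 gives the estimator and decision rule: "A 95% two-sided confidence interval for the mean of KSS Objective Knee Score at 2 years will be computed". A lower bound above 81 supports non-inferiority; a lower bound above 86 supports a claim of being better than 86.

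The missing-data plan in section 8.3 is one sentence: "No missing data will be imputed". Section 8.4.2 sizes the test and adds an allowance for loss: "After factoring a 30% attrition rate, a total of 46 cases will be needed".

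The Evaluation Schedule requires the postoperative functional evaluation, which contains the 2011 KSS, at 6 weeks, 6 months, 1 year, 2 years and 5 years. The eCRF grid in Appendix G repeats this, and the Objective Knee Score is a derived field on the postoperative KSS form. Under section 8.4.1, data not needed for an objective are only summarised by visit. No longitudinal model and no missing-data sensitivity analysis is given for this test.

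Section 8.4.4 defines the per protocol population as subjects who, among other conditions, "are available for efficacy evaluation at the 2-year primary endpoint". It assigns the primary and secondary efficacy analyses to that population and is silent on the exploratory analysis. Section 4.3 ends participation when all implanted cones are removed for any reason.

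**The concern.** A mean at one visit, with nothing imputed, can draw only on cases that have a score at that visit. It estimates the mean of the implanted central-cone cases only if loss is unrelated to how the knee is doing. The three earlier scores could show whether the cases lost were already doing worse, and could correct for it, but the test does not use them.

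Some loss is tied to outcome by design: a case whose cones are all removed before 2 years leaves the study and has no 2-year score. If worse knees leave more often, the available-case mean is too high and the lower bound clears 81 more often than the nominal 2.5% allows. The objective is exploratory, but it has its own hypothesis, decision rule and sample size, and it permits a claim of being better than 86.

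**Working it through.** **Inputs from the documents.** Threshold 81 (section 8.1.7). From section 8.4.2: mean 86, SD 10, 32 evaluable cases, 80% power, margin 5, one-sided 2.5%, attrition 30%, total 46.

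**Inputs that are assumptions.** The documents do not give the correlation between the 1-year and 2-year scores, the relation between loss and score, or the gap between cases lost and cases kept. The 30% is a planning figure, not an observed rate.

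**1. The plan's own figures.** n = [SD × (z0.975 + z0.80) / margin]² = (10 × 2.8016 / 5)² = 31.4, so 32. Then 32 / 0.70 = 45.7, so 46. Both reproduce. With a one-sample t-test, power at n = 32 is 78.2% (80.7% by the normal approximation), close enough to the stated 80%.

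**2. Bias in general.** Let d be the share lost, C the mean of those kept, and C − D the mean of those lost. The full mean is (1 − d)C + d(C − D) = C − dD, so the available-case mean is too high by dD. The chance of wrongly passing when the full mean is exactly 81 follows from the noncentral t with n = 32 and SD 10:

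| D (points) | Bias at d = 0.30 | Chance of passing at a true mean of 81 |
|---|---|---|
| 3 | 0.3 × 3 = 0.9 | 7.1% |
| 5 | 0.3 × 5 = 1.5 | 12.8% |
| 10 | 0.3 × 10 = 3.0 | 37.6% |

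With only 10% lost and D = 10, the bias is 0.1 × 10 = 1.0 and the chance is 9.1% (n = 41).

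**3. Loss driven by the 1-year score.** The simulation used 46 cases, normal 1-year and 2-year scores with SD 10, a true mean of 81, and logistic dropout on the 1-year score set to 30% overall. The available-case t-interval was compared with the likelihood estimate for this two-visit pattern, which is the regression of the 2-year on the 1-year score evaluated at the full-sample 1-year mean.

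| Dropout odds per 10 points lower at 1 year | Correlation | Available-case bias | Available-case false-positive rate |
|---|---|---|---|
| ×2 | 0.6 | +1.15 | 9.1% |
| ×2 | 0.5–0.7 | +0.97 to +1.34 | 8–11% |
| ×3 | 0.5–0.7 | +1.4 to +1.9 | 12–19% |

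At correlation 0.6 with doubled odds, the likelihood estimate has bias of about 0 and a false-positive rate of 2.7%. Over a wider grid (correlation 0.3 to 0.7, log-odds 0.5 to 1.5 per SD), available-case bias runs from 0.4 to 2.3 points and the false-positive rate from 4.1% to 26.3%. The likelihood estimate stays within 0.05 points and at 2.5% to 2.8%. If loss is completely random, its standard error is 3% to 8% smaller.

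**4. Opposite direction.** If better knees are the ones lost (doubled odds, correlation 0.6), available-case bias is about −1.1 and the false-positive rate about 0.4%. The plan's test is then conservative.

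**5. Loss driven by the unseen 2-year score.** With doubled odds and correlation 0.6, available-case bias of +1.93 falls only to +1.29 with the likelihood estimate. The earlier scores remove part of the bias, not all of it.

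**6. The reference value.** Section 8.4.2 takes 86 from this study's existing data on the other cones. Suppose 86 is itself an available-case mean that is 1.14 points too high, and the cones are truly equal. The true mean is then 86 − 1.14 = 84.86, which is 3.86 above 81 rather than 5. With the likelihood standard error of 1.678, power is about 61%, compared with the 78% in step 1.

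**The case against.** The case for leaving the plan alone has real substance.

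- **The objective is exploratory.** It concerns 40 to 50 cases, and the primary result on revision for aseptic loosening does not depend on it. This stands.
- **The size is assumed.** Nothing in the documents shows that worse knees leave. Section 4.3 also lists death and centre termination as exits, section 13.3 mentions loss of insurance, and the protocol provides for tracing and visit reimbursement. A reader might infer that the plan forecasts 14 missing cases or that the test will pass too often. The documents support neither: 30% is a sample-size allowance, and the direction of any bias is unknown.
- **The near-zero bias of the likelihood estimate follows from the setup.** Dropout was generated from the very score the estimator uses; step 5 shows what happens otherwise. The check also used two visits, not the full four-visit model. Both points stand, so the model alone is not enough.
- **The reference may carry the same selection.** If 86 is an available-case mean under similar loss, much of the bias could cancel in the comparison, and correcting only one side would make the test too strict. The documents do not say how 86 was derived, so this is open.
- **A model on all implanted cases implicitly projects a 2-year score for knees whose cones were removed and for patients who died.** This stands and needs an explicit rule.

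A reader might also carry the point over to the 2-year LEAS and HSS Patella comparisons in section 8.4.1. That does not fit. Those compare two studies, where applicable, with adjustment for the preoperative score, age, gender and BMI, and the documents do not show that visit-level data from the other study will be used.

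Nor does section 8.4.4 restrict this test to completers. That reading is reasonable, given a single-visit mean with no imputation, but it is inferred.

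**Conclusion.** The concern holds conditionally. As written, the central-cone test rests on available 2-year scores and ignores three earlier measurements of the same score. If loss is related to those earlier scores, the mean is biased, and upward if worse knees leave. With 30% loss, SD 10, correlations of 0.5 to 0.7 and dropout odds doubling per 10 points lower at 1 year, the bias is about 1.0 to 1.3 points, or 20% to 26% of the 5-point margin (1.0/5 and 1.3/5). The one-sided false-positive rate is then about 8% to 11% instead of 2.5%.

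The correlation and the dropout pattern are assumptions, and the reverse pattern would make the test conservative. The case for change does not depend on the direction: a likelihood-based model corrects either one when loss depends on observed scores, and it is somewhat more precise when loss is random. It is only a partial remedy when loss depends on unseen scores. The planned 32 and 46 are arithmetically sound, and the primary conclusion is not affected.

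**What to change.** In section 8.1.8:

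1. Estimate the 2-year mean and its 95% confidence interval from a likelihood-based repeated-measures model on all implanted central-cone cases. Use KSS Objective scores at the visits to 2 years, visit as a factor, unstructured covariance and Kenward-Roger degrees of freedom. Compare the lower bound with 81. The model imputes nothing, so it is compatible with section 8.3.
2. Keep the available-case interval as a sensitivity analysis.
3. Add a delta-adjusted (tipping-point) sensitivity analysis for loss that depends on unobserved scores.
4. State how cases terminated for cone removal, or lost to death, before 2 years are counted.

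In section 8.4.4, name the population for the exploratory analysis. In section 8.4.2, state whether 86 was an available-case mean; if it was, re-derive it by the same model.

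**Cost.** SAP wording, one PROC MIXED step and one sensitivity analysis. No new data are collected and the planned 46 does not change. The model relies on data being missing at random, which is a weaker condition than the available-case mean needs. If 86 is an available-case mean and is not re-derived, the test becomes harder to pass than intended.
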